In a pilot study conducted in the Emergency Department, Queen Elizabeth University Hospital (20/NS/0064), the Thales High Temperature Detection (HTD) system was found to be more accurate than a tympanic thermometer (Ref) which captures Infrared radiation emitted by the tympanic membrane in the ear. (Figure 1) or forehead thermometer. Tympanic temperature measurements are typically used in the hospital setting in Scotland whereas forehead IR measurement is common in transportation and workplace settings.

[figure not shown]

Figure 1: Distribution of variance between measurements for each subject for tympanic thermometer and HTD (n = 80)

The HTD has been redesigned in response to three key findings from the pilot study:

- The relative temperature of some facial features correlated more strongly with tympanic temperature than others.
- Having an external Black Body (BB) calibration source in the scene at all times was impractical in a clinical environment
- Camera systems require to be compact and portable to be useful to clinical staff.

As a result, the HTD is now significantly reduced in size, including peripheral devices. A novel calibration solution has been designed (and patented) that not only removes the need for the black body source but allows for a more accurate temperature evaluation. In addition, facial feature detection has been integrated into the software to allow it to automatically locate the patient's head and in the near future, automatically determine the temperatures of individual facial features. This development will capture facial feature detection – not facial recognition.

[figure not shown]

Figure 2: Temperature Measurement vs Actual

Figure 2 shows that the thermometer (juniper) in forehead mode appeared to return measured temperature + an offset to estimate core. The HTD can be calibrated in the same way i.e. to use the actual forehead temperature returned from the HTD plus the same offset. For tympanic comparison, the maximum temperature returned by the HTD (probably the canthus) correlates best – but it is still likely that some post processing will be required to ensure that a direct comparison can be made.

2. Aims

The Thales HTD (High Temperature Detection) System is a thermal camera based, human temperature measurement system.

This study will compare the HTD system with the two routinely used temperature measurement systems (tympanic and forehead) to understand the level of agreement that can be achieved and so its potential utility in triage and in a transportation and workplace setting. A secondary objective of this study are to assess if skin tone adds any additional differences

between a thermal camera based system temperature assessment and the routinely used tympanic and forehead based methods.

If results are encouraging the aim would then be to undertake a clinical investigation in order to get CE marking for use in a clinical setting.

100 staff and 100 patients will be consented with thermal images of their face taken as well as having their temperatures taken. The following measurements and information will be recorded:

- Forehead temperature from the HTD System
- Head temperature from the HTD System
- Tympanic temperature from a tympanic IR thermometer
- Forehead temperature from a forehead IR thermometer
- Age
- Ethnicity

A sample of size 100 will give 95% confidence intervals for the limits of agreement of +/- 0.34 standard deviations (<https://www-users.york.ac.uk/~mb55/meas/sizemeth.>). These limits of agreement will then allow determination of how close the temperature readings are between 1. Tympanic vs. HTD and 2. Forehead vs HTD and whether or not these are within +/- 0.2 degrees. It will demonstrate if there is a trend over the temperature range to understand consistency. The bias will be quantified using the mean difference (significance determined using a t-test).

The larger sample size (200) is proposed to gather a wider range of skin tone measures. Staff members will be recruited in addition to patients as this is likely to increase the diversity of the sample.

Although a BB source is not required for the new HTD system, a BB will be housed in the room where staff measurements are taken. Its inclusion gives another source of ground truth and will allow the calibration of all systems to be checked at regular intervals throughout the study.

3. Research Questions

Primary

- To determine the diagnostic accuracy of HTD for the measurement of fever, using an equivalence comparison with the maximum temperature recorded with two routinely used temperature measurements (tympanic and forehead), margin $\pm 0.2^{\circ}\text{C}$.

Secondary

- To determine if skin tone is an independent confounding factor in the measurement of fever using HTD
- To establish performance of internal calibration of Thales device
- To power for a definitive Clinical Investigation to determine clinical efficacy and safety cut off with HTD

4. Study Design

Patient Identification

Two groups will be identified

1. Patients who present to the Emergency Department (ED) in QEUH will be approached either by ED nurses or clinical fellows they can approach reception staff/nurse directly for information after reading posters on the ED wall.
2. QEUH ED staff will be approached either by ED nurses or clinical fellow.

Inclusion criteria

- *Patients ≥ 16 years old with no upper age limit*
- *Patients able to read and understand English*
- *Patients able to give informed consent*
- *Patients being triaged through ED for any complaint (not necessarily COVID-19)*
- *QEUH ED staff*

Exclusion criteria

- *Patients not meeting the inclusion criteria*
- *Patients who do not have capacity to consent*
- *Patients attending ED who are fast-tracked without triage*

Consent

Participants will be given a participant information sheet (PIS v2) to read while they are in waiting to be triaged (patients) or working in the ED (staff). There will be posters displayed publicising the study, and if people are interested they can ask reception staff or a nurse for more information. The nurse or fellow will go through the PIS and provide opportunity to ask questions. Due to the circumstances there is no opportunity for patients to take the PIS away and discuss it with friends/family which would be preferred. If the patient/staff member wishes to participate, a consent form will be provided which has some statements to agree to and sign. The participant can keep a copy of the signed consent form as well as the PIS. Failure to consent will not change clinical care for patients.

The PIS will make it clear that Thales will hold a copy of the identifiable images for a maximum of 1 year. Thales will securely store and analyse visible and thermal data required for future algorithm upgrades. It is anticipated that Thales will require to hold onto both visible and thermal data long enough to be required for regulatory purposes. For example, it is anticipated that the thermal data, and associated metadata, will be required for a maximum of ten years and the visible data for a maximum of one year, after which time the data will be securely destroyed.

Study procedures

After the participant has consented to take part, the research will take a front view with the thermal imaging camera. The following data is routinely collected at triage and a copy of the data will also be entered into the Thales electronic Case Report Form (eCRF). No patient name or personal details will be held by Thales.

- Temperature
 - Oral
 - IR Forehead
 - Ear
- History of Fever Y/N
- Age
- Ethnicity
- If they are wearing contact lenses

While desirable to have uncovered face thermal images, it is accepted that some patients may choose to wear facemasks. Patients will be asked to remove spectacles.

It is expected that the thermal imaging system will sit on a table or worktop and image patients approximately 1.5m to 2.0m away. The system will require access to a mains wall socket. The kit will remain set up in a locked room when not being used.

The system will comprise of:

- Surface Pro Tablet PC;
- Thales camera mounted on a portable tripod;
- Thermal calibration Black Body source (for calibration validation purposes only).
- MiFi internet connection
- Forehead thermometer
- Tympanic thermometer

The tablet will auto-run easy to use software allowing hospital staff to record:

- Thermal and TV image of the patient front on;
- Non-personal patient metadata:
- Patient temperature measured by existing clinical methods

The system will be simple to use and aims to minimise the disruption of the QEUH staff. Thales will have provided training of QEUH staff on how to operate the equipment and support of the equipment during the data collection activity. Training will take the form of a pdf, training video and if required a video conference call.

Follow Up

There is no follow up required – patients are only required to commit to one hospital visit when they initially present at ED and have their picture taken with the thermal imaging camera. Staff will require only to have their picture taken.

5. Withdrawal

If participants wish to withdraw their consent after the intervention (after the image has been taken) they can do so and it will not affect their clinical treatment. They may withdraw from the study at their own request and are not required to give a reason for this. They will be made aware that this will not affect their future care. Participants will be made aware that should they withdraw the data collected to date will be retained and used in the final analysis.

6. Data handling, analysis and archival

Data Handling

All the information obtained about participants in the course of the study is confidential and will be held in accordance with the General Data Protection Regulation (GDPR 2018). Data will be entered into a custom graphical user interface (GUI). Once the images and metadata have been recorded they will be regularly and periodically encrypted and then the unencrypted images deleted from the device automatically. Encrypted data will be synced with an encrypted dropbox and then transferred to Thales secure servers. Data will be unencrypted when it reaches the secure Thales servers.

Data are stored on dedicated storage area implementing Mandatory Access Control for an explicit list of authorised users. The management of those IT resources are performed by Thales UK Ltd. Thales UK Ltd is certified against the Cyber Essential Plus scheme.

Data Analysis

Personal data will be collected and processed only for the purpose of answering the research questions. The thermal images are Personally Identifiable Information (PII) and will be retained by the company for as short a time as possible before being permanently deleted. The other data items are not PII and are low risk in terms of identifying the patient from anonymised data. Personal information will not be shared with anybody outside the study.

The feasibility study data will primarily be analysed using statistical methods looking for relationships between facial feature temperatures and patient metadata. Artificial Intelligence (AI) /Convolutional Neural Network (CNN) based feature detection algorithms *may* be used to find the coordinates of the key points on the face in the visible image. The corresponding coordinates can be found with fine camera alignment and calibration. The thermal features may then be extracted for analysis along with the patient metadata. A manual feature extraction method may be used instead of the AI/CCN method if deemed more efficient for the smaller, initial dataset of 200 patients. Manual inspection of thermal images will be used to look for patterns and anomalies.

Three readings will be done per participant and comparisons done between:-

1. Tympanic vs. Thermal
2. IR vs. Thermal

A sample of size 100 will give 95% CIs for the limits of agreement of +/- 0.34 standard deviations (i.e. about a third of the standard deviation)

A sample of size 200 will give 95% CIs for the limits of agreement of +/- 0.24 standard deviations (i.e. about a quarter of the standard deviation)

Accuracy for other pre-defined sample sizes can be computed as +/- $1.96 \sqrt{3/n}$ as the multiplier of the standard deviation.

Data Archival

The participants will be allocated a unique ID number. Hardcopies of patient consent data and the patient identity/ study identifier key will be held in the ED site file and archived locally when the study is finished.

Only authorised research personnel will have access to the data collected in this study. They may also be looked at by representatives of regulatory authorities and by authorised people from NHS Greater Glasgow & Clyde and if an audit is required for quality assurance purposes. All will have a duty of confidentiality to research participants.

7. Regulatory & Ethics Committee Approval

The study shall not commence until the study protocol, information sheet and consent form have been reviewed and approved from a Research Ethics Committee and relevant NHS permission is obtained.

The sponsor will be responsible for deciding whether any protocol amendments are substantial and non-substantial in collaboration with the Chief Investigator. Where an amendment is required to study documentation that requires REC approval, changes will not be implemented until REC approval is received and local permission confirmed. Should an amendment be required to eliminate an apparent immediate hazard to participants this may be implemented immediately and the REC and R&D notified as soon as is possible. Minor amendments for logistical or administrative purposes may be implemented immediately. Amendments will be logged on the Sponsor's Study Amendment Log and stored in the Trial Master/Site File(s).

Annual Progress Reports shall be submitted to the REC within 30 days of the anniversary date on which the favourable opinion was given – until the end of the study. A final report shall (where possible) be submitted to the REC within one year after the end of the study. If the study is terminated prematurely the CI will notify the REC, including the reasons for premature termination.

8. Data protection and patient confidentiality

All study staff and investigators will comply with the principles of the Data Protection Act 2018 in protecting the rights of study participants with regards to the collection, storage, processing and disclosure of personal information and will uphold the Act's/Regulations core principles.

Each participant will be assigned a study identity number, for use on all trial documents and the electronic database. Other than the identifiable images, no personally identifiable information will be stored. The identifiable images will be deleted as soon as possible – but certainly within 1 year. However, for the avoidance of doubt, all other unidentifiable images will be stored for up to 10 years. Very limited research data is required and this will be stored using the study identity number. Thales will not hold a key. The site will hold the key within the local site file until to link the images and the data, and this will be archived locally.

All data will be automatically encrypted shortly after acquisition. Original, unencrypted images will be securely deleted. All encrypted data will be held on the password protected tablet PC during the trial for backup purposes. All encrypted data will be synced with an encrypted

Thales Thermography Study Protocol: V2 09.09.20

dropbox. The encrypted data will be placed on secure Thales servers and stored within password protected folders. Data will then be unencrypted for analysis.

Personal data will be stored for 10 years following the end of the study, so that the Chief Investigator may provide participants with a summary of the research (should they wish to receive a copy). Data generated as a result of this study will be available for inspection on request by NHS Greater Glasgow & Clyde, the REC, local R&D Departments and the regulatory authorities.

9. Indemnity

Insurance and indemnity for trial participants and trial staff is covered within the NHS Indemnity Arrangements for clinical negligence claims in the NHS. There are no special compensation arrangements, but trial participants may have recourse through the NHS complaints procedures.

10. Dissemination of results and publication

If results are encouraging the aim would then be to undertake a clinical investigation in order to get CE marking for use in a clinical setting - with a fever "yes/no" result. Nonetheless preliminary results may be publishable in a peer reviewed journal.

11. References

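### Does the protocol define the HTD value in conflicting ways, leaving the bias test and the ±0.2 °C comparison unsettled?

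*Protocol*

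**What the plan says.** The background text after Figure 2 discusses the two thermometers separately. For the forehead device, the HTD can be calibrated "to use the actual forehead temperature returned from the HTD plus the same offset". For the tympanic device, "the maximum temperature returned by the HTD (probably the canthus) correlates best", with the caution that "it is still likely that some post processing will be required to ensure that a direct comparison can be made".

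Section 2 (Aims) lists two HTD quantities among the items recorded: a forehead temperature and "Head temperature from the HTD System". It then asks "how close the temperature readings are between 1. Tympanic vs. HTD and 2. Forehead vs HTD" and whether the limits of agreement lie within ±0.2 °C. On bias it says: "The bias will be quantified using the mean difference (significance determined using a t-test".

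The primary question in section 3 is an "equivalence comparison with the maximum temperature recorded with two routinely used temperature measurements (tympanic and forehead", with margin ±0.2 °C. Section 6 (Data Analysis) says "Three readings will be done per participant and comparisons done between" tympanic and thermal, and IR and thermal.

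**The concern.** Read quickly, the sections seem to describe different measurements. The background needs one HTD value per thermometer, one with an offset and one probably processed. Section 2 mentions neither adjustment. Section 6 appears to set one thermal value against both thermometers. The primary question sets an unnamed HTD value against the higher of the two thermometer readings, a reference to which the background matches neither HTD value.

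The mean difference moves one-for-one with any offset. The t-test of bias, and an equivalence test on the mean if one were done, could therefore give different answers for a raw maximum, a processed maximum or a single common value. In the extreme case, an offset estimated from the same participants' tympanic readings would make the mean difference zero whatever the device does.

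**Working it through.** **1. The passages side by side**

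| Place | HTD quantity | Compared with |
|---|---|---|
| Background, after Figure 2 | forehead plus the thermometer's offset | forehead thermometer |
| Background, after Figure 2 | maximum, probably the canthus, likely processed | tympanic thermometer |
| Section 2 | forehead; head | forehead; tympanic |
| Section 3, primary | HTD, value not named | higher of the two thermometers |
| Section 6 | Thermal | tympanic; IR |

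The background has two values and two comparisons, and so does section 2. The background also says that the software now locates the patient's head, with individual facial features to follow. A head temperature taken as the maximum over that region is a natural reading, though the protocol does not state it.

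Section 6 does not say that there is only one thermal value. Section 4 (Study procedures) describes a front-view image, and one such image can yield both a forehead and a head temperature. So one reading per device would not reduce the HTD to one number, and three replicates would create no conflict either. Three readings might also mean the three clinical temperatures listed in Study procedures (oral, IR forehead, ear). The phrase is unclear, but no reading of it forces a contradiction.

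**2. The plan's own precision figures**

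Section 6 gives the half-width of the 95% CI for a limit of agreement as 1.96·√(3/n) SDs.

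- n = 100: 1.96·√0.03 = 0.339, stated as 0.34.
- n = 200: 1.96·√0.015 = 0.240, stated as 0.24.

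Both reproduce. They are in SD units, so a constant offset leaves them unchanged.

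**3. What an offset could do to the mean**

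The protocol gives no SD of differences, so 0.3 to 0.5 °C is assumed, with n = 200. The half-width of the 95% CI of the mean is t(0.975, 199)·SD/√200.

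| | SD 0.3 | SD 0.5 |
|---|---|---|
| Half-width (°C) | 0.042 | 0.070 |
| CI inside ±0.2 if the absolute mean is at most | 0.158 | 0.130 |
| CI wholly outside from | 0.242 | 0.270 |
| P(CI inside), net bias 0 °C | 100% | 100% |
| P(CI inside), net bias 0.1 °C | 99.7% | 80% |
| P(CI inside), net bias 0.2 °C | 2.5% | 2.5% |
| P(CI inside), net bias 0.3 °C | 0% | 0% |

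The probabilities come from 200,000 simulated trials per cell. The gap between just inside and wholly outside is only 2 × 0.042 = 0.084 °C or 2 × 0.070 = 0.14 °C, but that applies to a mean already at the edge. Starting from no bias, a shift of 0.242 or 0.270 °C is needed to put the CI wholly outside. Nothing in the protocol shows that shifts of either size would arise.

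**4. What an offset does to the criterion in section 2**

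Section 2 ties ±0.2 °C to the limits of agreement. They fit only if |mean| + 1.96·SD ≤ 0.2, so even at zero bias SD must be at most 0.2/1.96 = 0.102 °C. At SD 0.3 the limits are ±0.588 °C around the mean, and at SD 0.5 they are ±0.98 °C. They miss with or without an offset.

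**5. The maximum as reference**

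Suppose the two thermometers have equal means and their difference is normal with SD s. An HTD value matched exactly to tympanic then lies on average 0.399·s below the higher reading: 0.120 °C at s = 0.3 and 0.199 °C at s = 0.5. This gap comes from choosing the higher of two readings as the reference. Clearer labelling of the HTD value would not remove it.

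**The case for a change.** The best case for acting is that the primary comparison is the one that matters most, and no section says which HTD value enters it. The background is the only text that says which value suits which thermometer, and the later sections do not repeat it. An analysis plan could fill the gap without changing the protocol's wording. An equivalence comparison with a ±0.2 °C margin is also readily understood as a test on the mean, and that is where an offset counts.

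Part of this stands. The primary question does leave the HTD value unnamed, and both head and three readings could be clearer. The arithmetic on the mean is also correct for the assumed SDs.

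The claim of contradiction does not stand. The background sentences are conditional: they say what can be done and what is likely, and they do not lay down the analysis. For the forehead comparison they already give the source of the offset, namely the thermometer's own. The exact region, the form of processing and the names of derived variables are details that an analysis plan commonly settles, and that plan is not at hand. A mean-based verdict at ±0.2 °C is one reading of section 3, but the protocol does not define it. Nor does any section say that processing will be fitted to these participants, so the zero-by-construction case cannot be held against the plan. Reporting unprocessed and processed means together would be a reasonable preference, but leaving it out is no error.

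**Conclusion.** No change to the plan is called for. The sections are compatible on a natural reading: forehead HTD with the forehead thermometer, and head HTD (as the maximum) with the tympanic one. The wording leaves a gap that analysts can sensibly fill by recording, before the reference readings are analysed, which HTD value and which processing each comparison uses.

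For a constant offset, any effect is confined to the mean difference and the centre of the limits of agreement. Their width and the ±0.34 and ±0.24 SD precision are untouched. A different facial region or a regression-type correction could also change the SD, but the protocol does not commit to either. The size of the effect cannot be derived from the document, which gives neither an offset nor an SD of differences. The figures for the mean rest on assumed SDs of 0.3 to 0.5 °C and assumed shifts. At those SDs the ±0.2 °C criterion in section 2 fails whichever offset is used. Section 6 calls these feasibility data, and section 2 asks what agreement can be achieved before any clinical investigation, which lowers the stakes further.

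### Could post-processing of the HTD reading make the tympanic bias test empty?

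*Protocol*

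**What the plan says.** The background text before section 2 reports that "The HTD has been redesigned in response to three key findings from the pilot study" and that calibration is now done differently. In discussing Figure 2 it treats the two reference methods differently:

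- **Forehead:** the HTD forehead value is to receive the offset that the forehead thermometer itself applies.
- **Tympanic:** the HTD maximum is said to correlate best, but "it is still likely that some post processing will be required to ensure that a direct comparison can be made". No form or data source is given.

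The same text says the software will "in the near future, automatically determine the temperatures of individual facial features".

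Section 2 gives the agreement analysis for 100 patients and 100 staff: limits of agreement, judged by "whether or not these are within +/- 0.2 degrees", and then "The bias will be quantified using the mean difference (significance determined using a t-test". Section 3 poses the primary question against the maximum of the two thermometer readings. It also lists a secondary aim, "To power for a definitive Clinical Investigation".

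Section 6 (Data Analysis) calls this a feasibility study and plans to analyse the data by "looking for relationships between facial feature temperatures and patient metadata", with manual or automated feature extraction still open. The list of recorded items in section 4 (Study procedures) places "Patient temperature measured by existing clinical methods" after the metadata entry.

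**The concern.** One set of 200 people appears to have two roles. They may show how HTD readings should be converted to the tympanic scale, and they supply the bias and limits of agreement after conversion. The Protocol names no derivation subset, cross-validation or algorithm freeze. The pilot data may not carry over, because the device and its calibration have changed since.

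If the conversion were estimated in the people analysed, the tympanic mean difference would be zero whatever the device does. A reader could take that zero as evidence of accuracy. If features were also chosen in the same data, the limits would be too narrow, and this could carry into the size of the definitive investigation.

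**Working it through.** **Inputs.** From the Protocol: n = 200 (section 2), margin ±0.2 °C (sections 2 and 3), and precision of the limits of agreement 1.96·√(3/n) SD (section 6). Assumed, because the Protocol gives no values: SD of HTD-minus-tympanic differences 0.3 or 0.5 °C; true bias up to 1.0 °C; two-sided 5% t-test; for the regression case, reference SD 0.6 °C and HTD slope 0.8.

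**1. The Protocol's own figures.** 1.96·√(3/100) = 0.339 and 1.96·√(3/200) = 0.240. Both stated figures (0.34 and 0.24) are reproduced.

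**2. Effect of an in-sample offset on bias.** Let d = HTD − tympanic. Subtracting the sample mean of d gives differences with mean exactly 0, so t = 0. Least-squares residuals from a line with an intercept also sum to zero. Simulation at n = 200, 1,500 runs per setting:

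| True bias (°C) | t-test rejects, no fit | t-test rejects, fitted in-sample | Mean equivalence within ±0.2, no fit | Same, fitted in-sample |
|---|---|---|---|---|
| 0 | about 5% | 0% | 100% | 100% |
| 0.2 | 100% | 0% | about 4–5% | 100% |
| 0.5 and 1.0 | 100% | 0% | 0% | 100% |

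For a bias of 0.1 °C, the unfitted test has power 80.4% at SD 0.5 and 99.7% at SD 0.3 (noncentral t). So the conditional claim is right.

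**3. Effect on the limits of agreement.** An offset is a constant, so the SD of d and the width of the limits do not change. At SD 0.3 the half-width is 1.96 × 0.3 = 0.59 °C. Limits within ±0.2 °C at zero bias need SD ≤ 0.2/1.96 = 0.102 °C, so the fit does not make that criterion pass. With a one-feature line, the in-sample SD was 0.317 against about 0.319 in people not used for fitting, and 0.431 against about 0.434. That is under 1% too narrow. One percent of a 1.96 SD half-width is 0.02 SD, against a stated precision of ±0.24 SD.

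**4. Effect on the other comparisons.** The forehead rule uses an outside offset, so it is untouched. For the primary question, write T for tympanic and F for forehead: max(T, F) = T + max(F − T, 0). An HTD reading with zero mean difference from T therefore differs from the maximum by −mean[max(F − T, 0)], which is not zero in general. That mean would then depend on the two thermometers alone. This applies only if the tympanic-fitted reading were carried into the primary comparison, which the Protocol does not say.

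**5. Price of a split (derive in 100, test in 100).** Precision of the limits goes from ±0.24 to ±0.34 SD. The bias interval goes from 1.96/√200 = ±0.14 SD to 1.96/√100 = ±0.20 SD. The test also picks up derivation error: the mean difference has variance SD²/100 + SD²/100, twice what the t-test assumes. An on-average unbiased rule is therefore rejected with probability about 2[1 − Φ(1.96/√2)] = 2[1 − Φ(1.386)] ≈ 17%. The simulated range was about 15–17%.

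**The case for a change.** The strongest opposing case is that whether participants are set aside is a design decision. It fixes the evaluation sample and must be taken before HTD and reference readings are compared, so it belongs in the Protocol. The Protocol itself announces a conversion that is not yet fixed and plans exploration of the same data. After the redesign, the pilot is not an assured source.

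Part of this stands. The text would permit an in-sample fit, and a test that cannot fail must not be reported as evidence. But a set-aside becomes a design decision only if in-sample fitting is intended, and no section says so. The sentence is a background remark describing what had already been observed, beside a forehead rule with an outside offset. Uncertain carry-over from the pilot is a reason to check the mapping; it does not show that the mapping will be fitted in the study.

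The feature-selection part is weaker. Understatement of the SD by 4.1% to 6.9% (best of 3 to 10 features), or 1.7% to 5.1% (3 to 10 fitted jointly), rests on assumed feature counts and SDs. The Protocol names the HTD maximum for the tympanic comparison, and the section 2 list records only a forehead and a head value from the HTD. The search in section 6 is not described as the source of the tympanic conversion, and section 4 (Consent) links the stored images to future algorithm upgrades.

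**Conclusion.** No change to the plan follows. The algebra holds if an offset or intercept is fitted and tested in the same people, but the Protocol does not state that this will happen. What it lacks is the form, source and locking of one processing step, which is detail commonly fixed in a statistical analysis plan.

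If the fit were made in-sample, the loss would fall on the tympanic mean difference, its t-test and any mean-equivalence claim built on it, including the primary comparison if it reused the fitted reading. The limits of agreement would remain sound: unchanged in width for an offset, and under 1% too narrow for a one-feature line at the assumed SDs. An analyst who had to estimate the conversion in the study could report the bias of the unprocessed HTD reading beside the processed one, or cross-validate, and keep all 200.

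Splitting the sample is a poor exchange for a problem that may not arise, since section 2 justifies 200 by the range of skin tones. The black-body source in section 2 gives a calibration check that does not depend on the tympanic test. The later clinical investigation foreseen in sections 2, 3 and 10 offers a separate evaluation.
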